5.1 Subject Inclusion Criteria

Subjects should meet all of the following inclusion criteria

1. Male or female age ≥ 12 years.
2. Recipient of a solid organ or hematopoietic stem cell transplant.
3. Positive test result for Norovirus within 14 days of enrollment that is obtained as part of routine clinical care using a Norovirus testing available to the site.
4. Active GI symptoms (diarrhea or vomiting) that, in the opinion of the PI, are secondary to Norovirus.[#]
5. Willing and able to provide written informed consent and assent before initiation of any study procedures, consistent with local IRB policy.
6. Subjects must be of non-childbearing potential or if of childbearing potential, must be using an effective method of birth control or must be abstinent.
 - Non-childbearing potential is defined as surgically sterile or postmenopausal for $>$ one year.
 - Effective methods of birth control include the use of hormonal or barrier birth control such as implants, injectable contraceptives, combined oral contraceptives, intrauterine devices [IUDs] or condoms with spermicidal agents during study period. Female subjects must be using an effective method of birth control or practice abstinence and must agree to continue such precautions during the study and for 30 days after the Day 28 study visit.
 - A woman is eligible if she is monogamous with a vasectomized male. This subject is considered low risk and not required to use contraception.
7. Agrees to complete all screening requirements, study visits and procedures.

[#] Patients must have active diarrhea, which is defined as at least 3 days of Bristol 6 or 7 stools in the past 2 weeks prior to enrollment per patient report.

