5.2 Subject Exclusion Criteria

Subjects meeting any of the exclusion criteria at baseline will be excluded from study participation

1. Other identified infectious causes of diarrhea at screening*.
2. Any condition that would, in opinion of the Site Investigator, place the subject at an unacceptable risk of injury or render the subject unable to meet the requirements of the protocol.
3. Subjects receiving oral or intravenous immunoglobulin therapy concurrently or in the 14 days prior to enrollment.
4. Nitazoxanide use for any illness in the previous 30 days prior to randomization.
5. Have received experimental products within 30 days prior to the study entry or plan to receive experimental products at any time during the study
6. Known sensitivity to nitazoxanide or any of the excipients comprising the nitazoxanide tablets.
7. Subjects unable to swallow oral medications.
8. Subjects with ostomy.
9. Women who are pregnant or lactating or have a positive urine pregnancy test at screening/enrollment/Day 1.

Co-enrollment in other studies is allowed if none of the above exclusion criteria are met.

*Alternative diagnosis requiring treatment would be considered a co-infection; if the testing is positive for a pathogen that the PI does not feel is causing the symptoms, they may be included but the PI or his/her designee must document that the positive test is not clinically significant, does not require treatment and is not causing the symptoms making the patient eligible for enrollment.

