6 STUDY INTERVENTION/INVESTIGATIONAL PRODUCT

6.1 Study Product Description

Nitazoxanide is a synthetic antiprotozoal agent for oral administration. It is designated chemically as 2-acetyloxy-N- (5-nitro-2-thiazolyl) benzamide. The molecular formula is $C_{12}H_9N_3O_5S$ and the molecular weight is 307.3. The placebo will look identical to nitazoxanide, and will have the same inactive ingredients (described in section 6.1.2).

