4. Stool for Pathogen Screen: This assay will be performed in the Diagnostic Infectious Diseases Testing Laboratory (Cincinnati Children's Hospital Medical Center (CCHMC, Cincinnati, OH) which will be provided a 1-gram aliquot of stool from the [name] Laboratory. Day 1 stool specimen and non-formed stool samples from subsequent visits will be screened for additional pathogens (Bacteria- *Campylobacter* (jejuni, coli and upsaliensis), *Clostridium difficile* (Toxin A/B), *Plesiomonas shigelloides*, *Salmonella* species, *Yersinia enterocolitica*, *Vibrio* species (parahaemolyticus, vulnificus and cholerae), Diarrheagenic *E.coli*/*Shigella* including, Enteroaggregative *E. coli* (EAEC), Enteropathogenic *E. coli* (EPEC), Enterotoxigenic *E. coli* (ETEC), Shiga-like toxin-producing *E. coli* (STEC), *Shigella*/Enteroinvasive *E. coli* (EIEC); Parasites- *Cryptosporidium*, *Cyclospora cayetanensis*, *Entamoeba histolytica*, *Giardia lamblia*; Viruses - Adenovirus F40/41, Astrovirus, Norovirus GI/GII, Rotavirus A, Sapovirus (I, II, IV and V)) using the FDA-cleared FilmArray system from BioFire Diagnostics (bioMerieux, Marcy l'Etoile, France). After collection in the stool hat, the subjects can wipe down and disinfect the outside of the container and place it in a bag for transport then refrigerate until they come to their visit with the research staff. The sample must have been produced within 24 hours of the visit and if it exceeds 24 hours it must be disposed. Subject would be encouraged to provide another sample within the visit window and if not, a rectal swab may be used for virus detection.

Table 5: Protocol PRO Completion Guide

Phase	Treatment					Post-treatment monitoring							Unscheduled Visit	Early Termination Visit
	Screen Enroll Day 1	Day 7 (±3 d)	Day 14* (±3 d)	Day 21* (±3d)	Day 28 (+3 d)	Day 35 (±3d)	*Day 53 (±7d)	*Day 60 (±14 d)	*Day 113 ±7d	*Day 120 (±14 d)	*Day 173 ±7d	Day 180 (±14 d)		
Daily Diary		Days 1-7	Days 8-14	Days 15-21	Days 22-28			Days 29-60		Days 61-120		Days 121-180	X	Last week before term
Weekly Recall/ Phone Packet	X	X	X	X	X	X	X	X	X	X	X	X	X	X
Detailed PROs Packet	X				X			X		X		X		X

Daily Diary: To be completed by subject daily. Diary 1-28 days; Diary 29-180 days See MOP for details.

Weekly Recall Packet: To be completed by study staff. See MOP for details.

Detailed PROs Packet: To be completed by study staff. This will include PROMIS and QOL Questionnaires. See MOP for details.

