11 STATISTICAL CONSIDERATIONS

11.1 Study Hypotheses

A formal hypothesis test is planned to compare nitazoxanide to placebo with respect to the primary efficacy outcome measure. The time from randomization until clinical resolution of Norovirus for at least 48 hours through 180 days will be compared between the two study arms.

The null hypothesis is that there is no difference in time until clinical resolution between study arms, with a two-sided alternative. The test for primary efficacy hypothesis will be conducted using a Log-Rank test at the 5% two-sided level of significance.

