11.2 Sample Size Considerations

Sample size calculations assume a 50% reduction in the median duration of diarrhea for the nitazoxanide-treated group compared to those receiving placebo. The median diarrhea duration for the placebo group is assumed to be 135 days, while the median diarrhea duration for the treatment group is assumed to be 67.5 days. Given these assumptions, a sample size of 64 subjects in each arm (128 total) is required to achieve 90% power using the Log-Rank test. Accounting for a 20% attrition rate, final sample size will be 80 in each arm (160 total).

Though discouraged, the protocol allows for subjects in either study group to receive additional nitazoxanide after 28 days. Under the assumptions of treatment efficacy, additional treatment received by placebo subjects would reduce the median duration of symptoms for the placebo group to be closer to that of the nitazoxanide-treated group. It is assumed that subjects who would have the worst study outcomes (longest time to clinical resolution of diarrhea) will be the most likely to receive additional treatment. Subjects receiving additional treatment will be imputed as having the worst outcome (time to resolution censored at 180 days). Accounting for this imputation method, the power attained for the primary comparison was computed via simulation (R version 3.0.3). Estimated power is displayed in the following table, varying the proportion of subjects in each study group who receive additional treatment

		Proportion Receiving Additional Treatment in the Placebo Group						
		0%	5%	10%	15%	20%	25%	30%
Proportion re-treated in the nitazoxanide Group	0%	91.3%	91.6%	91.7%	91.6%	91.8%	92.0%	92.3%
	5%	91.4%	91.5%	91.6%	91.2%	91.2%	91.8%	92.5%
	10%	-	91.5%	92.0%	91.2%	91.8%	91.2%	92.2%
	15%	-	-	90.7%	90.7%	91.0%	91.6%	91.8%
	20%	-	-	-	87.3%	87.1%	87.0%	87.7%
	25%	-	-	-	-	74.0%	73.9%	75.2%
	30%	-	-	-	-	-	40.0%	40.9%

For example, if 15% of placebo subjects receive nitazoxanide, and 5-10% of subjects in the nitazoxanide-treated group receive additional treatment, the power is estimated to be 91.2%. Note that implausible scenarios (where substantially more nitazoxanide subjects receive additional treatment than do placebo subjects) have been omitted from the table.

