Number of Type 6 or 7 Stools:

The number of Type 6 or 7 stools through Day 28 will be defined as the sum of the responses to the quantitative Daily Diary Diarrhea Questions during the Treatment Phase (see above). Missing responses will be left as missing.

Number of Days of IV Hydration or Total Parenteral Nutrition (TPN) Therapy:

The number of days of IV hydration or TPN therapy will be defined as the number of days with a concomitant medication with any indication related to IV hydration or TPN therapy. A blinded review of the concomitant medication data will be performed by the Medical Monitor to identify medications that should be included in the analysis. Days prior to Day 1 will not be included in the calculation of the number of days. Medications that are ongoing after Day 28 will be censored at 28 days.

Co-pathogen Status:

Co-pathogen status will be determined by the BioFire stool pathogen screen on Days 1 and 180. Co-pathogen status will be determined on Days 7, 14, 21, 28, 60, 120, and with recurrent diarrhea if unformed stool is present on study day. Analyses will only include whether pathogens were detected or not and will not differentiate by co-pathogen type. The listing will include which co-pathogens were detected at each subject/visit ([Listing 18](#)).

Secretor Status:

Saliva is collected at screening to determine H type 1 secretor status (phenotyping), while a buccal swab is collected to perform FUT2 genotyping. Phenotype and genotype results will either be “secretor” or “non-secretor” for each subject.

Norovirus-Specific Immunoglobulins (Ig):

Results below the lower limit of detection (LLOD) will be imputed as $\frac{1}{2}$ the LLOD. Results above the upper limit of detection (ULOD) will be imputed as the ULOD.

Responders:

A subject is classified as a responder if he or she has a four-fold or greater increase in Norovirus-specific Ig titers compared to baseline (Day 1).

Study Day:

Study day will be reported as the number of days from randomization with the day of randomization reported as study day 1.

Days Post-Randomization:

Days post-randomization will be reported as the number of days since randomization; if an event began on the day of randomization, the days post-randomization is reported as 0.

Duration:

Duration will be reported as the difference between the start and end dates, inclusive of the day the event started.

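### An undetected Giardia or Cryptosporidium co-infection could add an antiparasitic effect to the symptom-based primary endpoint, and the SAP's co-pathogen flag is not defined in a way that would show it

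*Protocol*

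**What the plan says.** **The drug.** Protocol 6.1: "Nitazoxanide is a synthetic antiprotozoal agent for oral administration". Protocol 2.1 gives its US approval as diarrhea caused by Giardia lamblia and Cryptosporidium parvum.

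**Entry.** Protocol 5.1, criterion 3, needs a positive norovirus result "obtained as part of routine clinical care using a Norovirus testing available to the site". Criterion 4 needs symptoms that the PI attributes to norovirus. Protocol 5.2, criterion 1, excludes other infectious causes identified at screening and names no panel that must be run. Its footnote says that "if the testing is positive for a pathogen that the PI does not feel is causing the symptoms, they may be included". It goes on to require the PI to document that the finding is not clinically significant, does not call for treatment and is not the cause of the symptoms.

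**Central testing.** Protocol 8.2.1: "Day 1 stool specimen and non-formed stool samples from subsequent visits will be screened for additional pathogens". The BioFire panel covers both parasites, and also norovirus GI/GII. Samples are frozen, batched and shipped at least every other month (Protocol 8.2.3), so the result cannot decide entry.

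**Analysis.** The primary analysis (SAP 8.1) compares time to symptom resolution in the mITT population and takes no account of co-infection. SAP 3.3 on co-pathogen status: "Analyses will only include whether pathogens were detected or not and will not differentiate by co-pathogen type". It then promises a listing of pathogens by subject and visit (Listing 18). SAP 8.3 and the Table 34 shell add a co-pathogen analysis of the primary outcome, with Present, Absent and Any Status rows.

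**The concern.** The primary endpoint is no vomiting and no Type 6 or 7 stools. It does not show which organism was responsible. If some subjects carry a parasite that the drug treats, those on nitazoxanide may resolve faster than those on placebo even if the drug does nothing to norovirus. Randomization balances such subjects between the arms but does not remove this effect, which favours nitazoxanide.

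The planned co-pathogen analysis is the natural place to look, but its flag has four weaknesses:

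- **Timing.** Protocol 11.4.5 counts a co-pathogen found at any time point. SAP 8.3 allows a time-varying version. Neither ties status to the pre-dose Day 1 sample.
- **Dependence on outcome.** Between Day 1 and Day 180 the panel is run only on unformed stool (Protocol Table 6). Subjects who stay ill are screened more often and so have more chances of being classed as Present. The Absent row is then partly selected on the outcome.
- **Norovirus.** It is a panel target, and the Listing 18 shell shows it as an example under co-pathogen detected. No text says that it does not count. Read literally, almost every subject would be Present.
- **Type.** Giardia is pooled with every other target, although the protocol names only these two parasites as approved indications.

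**Working it through.** **1. The plan's own figure.** Inputs from Protocol 11.1 and 11.2: test "conducted using a Log-Rank test at the 5% two-sided level of significance"; "The median diarrhea duration for the placebo group is assumed to be 135 days"; nitazoxanide median 67.5 days; 180 days of follow-up; "a sample size of 64 subjects in each arm (128 total) is required to achieve 90% power using the Log-Rank test". With exponential times:

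- P(event by Day 180) = 1 − 2^(−180/135) = 0.603 on placebo and 1 − 2^(−180/67.5) = 0.843 on nitazoxanide; mean 0.723.
- Schoenfeld: 4(1.96 + 1.2816)²/(ln 2)² = 87.5, so 88 events; 88/0.723 gives 122 subjects.
- Freedman: (1.96 + 1.2816)² × (1.5/0.5)² = 94.6 events; 94.6/0.723 gives 131 subjects.
- The stated 128 lies between these. Power at 128 is 91.5% (Schoenfeld) or 91.4% (simulation), against 91.3% in the protocol's table at 0%/0% retreatment. 128/0.80 = 160.

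The sample size is reproduced, and this point does not affect it.

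**2. Size of the bias, planned trial.** The documents give no prevalence q, so 1–10% is assumed. For context only, Protocol Table 1 puts all other single diagnoses together at 10.0% (community onset) and 5.4% (hospital onset). The drug is assumed to have no norovirus effect, with a median of 135 days in both arms. Co-infected nitazoxanide subjects resolve at 2, 5 or 50 times the common hazard; 50 times is a median of 135/50 = 2.7 days. Co-infected placebo subjects resolve like the rest. Unstratified log-rank, N = 160, 20,000 runs:

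| q | Two-sided rejection at hazard × 2 / 5 / 50 | Median apparent HR |
|---|---|---|
| 0 | 5.1 / 5.0 / 5.1% | 1.00 |
| 1% | 5.0 / 4.8 / 5.4% | 1.00–1.01 |
| 2% | 4.9 / 5.0 / 5.5% | 1.02–1.03 |
| 5% | 5.3 / 6.1 / 6.9% | 1.04–1.08 |
| 10% | 6.6 / 9.9 / 12.8% | 1.07–1.18 |

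**3. Harsher and milder inputs, 64 per arm.** Here co-infected nitazoxanide subjects resolve with a 3-day median.

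| Scenario | q = 2% | 5% | 10% |
|---|---|---|---|
| Placebo co-infected resolve like others | 5% | 7% | 11% |
| Placebo co-infected never resolve by Day 180 | 6% | 11% | 27% |
| Norovirus must also clear; placebo like others | 4–6% | 4–6% | 4–6% |
| Norovirus must also clear; placebo never resolve | 5% | 6% | 11% |

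The HRs in the first two rows run over 1.03–1.06, 1.09–1.17 and 1.18–1.37 at 2%, 5% and 10%.

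**4. The trial as it ended, N = 31 (SAP 6.6).**

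- Expected co-infected: 31 × 0.02 = 0.6; 31 × 0.05 = 1.6; 31 × 0.10 = 3.1.
- Chance of at least one, 1 − (1 − q)^31: 47%, 80% and 96%.
- Rejection under the step 2 model: 5.6–5.8% at q = 5% and 5.3–6.6% at q = 10%, against 5.2–5.5% at q = 0. Under the first two rows of step 3, with 16 against 15 subjects, it is about 5% at 2%, 6–6.5% at 5% and 7–10% at 10%.
- SAP 8 drops subgroups with fewer than five subjects per arm. A parasite-positive row needs at least 10 positives in all; at q = 10% the chance of 10 or more among 31 is 0.06%.

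The SAP now uses a stratified Cox model in place of the log-rank test, so the rates at N = 31 are a guide, not exact.

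**The case against.** The strongest reply is that much of this is already handled. A parasite known to cause symptoms or need treatment keeps the subject out, because the footnote's condition must be documented. Every Day 1 stool is screened centrally. Listing 18 names the pathogens by subject. The Absent row of Table 34 leaves out anyone with a detected parasite, and losing other pathogens as well costs precision without letting the bias back in. Both secondary efficacy endpoints measure norovirus RNA, which an antiparasitic effect alone does not explain. A 3-day median treats norovirus as a bystander in every co-infected subject; if norovirus must clear too, rejection mostly stays nominal. The trial stopped at 31, and SAP 14.2 describes the updated analyses as primarily descriptive.

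Most of this stands and limits the size of the point. Four things remain. The footnote deals only with parasites that were found, not with subjects who were never tested. Listing 18 gives no treatment comparison. The Absent row mixes baseline status with later samples that depend on stool form and, as written, may be nearly empty because norovirus is not left out. The viral-load endpoints are secondary and do not correct the symptom endpoint.

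A reader might infer that an antiparasitic effect is being counted as norovirus efficacy, or that the SAP hides co-pathogen identity. The documents support neither. No prevalence or co-infected subject is reported, and identity is listed by subject.

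**Conclusion.** The point holds as a possible bias with a cheap check, not as a demonstrated one. No parasite test is mandated before randomization, the central result comes too late to exclude anyone, the primary analysis ignores co-infection, and the planned co-pathogen flag does not give a clean baseline comparison.

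Under the assumed prevalences, the bias is negligible at 2% or less. It becomes material only near 10% with a strong antiparasitic effect: rejection 9.9–12.8% at N = 160, apparent HR 1.14–1.18. The 11% at q = 5% and 27% at q = 10% (64 per arm) also require that no co-infected placebo subject resolves by Day 180 and that norovirus plays no part in the treated ones. At the actual 31 subjects, rejection stays near nominal and reaches about 10% only under those same inputs at q = 10%. Prevalence and speed of antiparasitic response are assumptions throughout.

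**What to change.** - **SAP 3.3.** For the treatment comparisons in Tables 34 to 36, define co-pathogen status from the Day 1 BioFire result on stool collected before the first dose, and state that norovirus does not count. Later detections stay in Listing 18.
- **SAP 8.1.1.** Report by arm the number of subjects positive for Giardia or Cryptosporidium on that Day 1 sample. If there are any, repeat the primary mITT stratified Cox analysis without them as a supportive analysis. If there are none, one sentence closes the question.

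No separate efficacy row for parasite-positive subjects is needed; the five-per-arm rule would almost certainly remove it.

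The cost is SAP wording and at most one extra set of table rows, from data already collected. Because status is fixed before dosing, the supportive analysis keeps the randomized comparison. The downside is a few subjects lost from that analysis only. In the planned trial, power from 128 evaluable subjects would fall from 91.5% to 91.0%, 90.1% or 88.5% if 2%, 5% or 10% were left out. With 31 subjects, power for an HR of 2 is about 37% before any exclusion, assuming the same event fraction.

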5.3 Treatment Assignment Procedures

5.3.1 Randomization Procedures

Enrollment of subjects will be done online using the enrollment module of AdvantageEDCSM. Approximately 160 subjects will be randomized into two treatment groups: active nitazoxanide and placebo with equal allocation (1 to 1 randomization) after providing consent and confirmation of eligibility based on the study inclusion and exclusion criteria.

The study will use a stratified, permuted block randomization scheme. Permuted block randomization is used to avoid the potential for serious imbalance in the number of participants assigned to each group, an imbalance that can occur in the simple randomization procedures.

Stratification will be by:

- Duration of Symptoms: onset of Norovirus-associated symptoms (diarrhea, nausea and/or abnormal appetite) < 14 days vs. \geq 14 days
- Transplant Type: solid organ vs. hematopoietic stem cell transplant
- Age Range: pediatric (12-17 years) vs. adult \geq 18 years

The randomization list will be computer-generated by statisticians at the SDCC using a stratified, permuted block randomization scheme and is included in the enrollment module for the trial. AdvantageEDCSM will assign each subject to a treatment group after the demographic, duration of symptoms, transplant type, and eligibility data have been entered into the system.

Each site will have a supply of two 60cc identical blinded bottles pre-labeled with randomization numbers, each containing 30 tablets, sufficient to treat a subject with 56 doses. The two identical containers will be packaged in the same plastic bag. Once a subject is assigned a randomization number, the corresponding bottles will be distributed to the subject.

5.3.2 Masking Procedures

All subjects will take either nitazoxanide or matching placebo twice daily for 56 doses. The placebo will be manufactured by Romark, L.C., Ltd. to match the appearance (color, size, with “CTM” imprints) of the active compound and will be dispensed in identical bottles. Bottles will be labeled in such a way that it will not be obvious to the care team or the subject which arm they have been randomized to. Bottles will be delivered to the site pre-filled containing either nitazoxanide or placebo and will have a unique number. At the time of randomization, the unique number will be assigned to the individual subject. No member of the study team will be aware of the arm that the subject has been assigned to unless the site PI specifically requests unblinding (see section 5.3.4).

Refer to the MOP for unblinding procedures, including emergency unblinding procedures (Section 5.2 of MOP).

